#### 6.13.2. Subgroup Analyses for Hypoglycemic Events

For the documented symptomatic hypoglycemia based on the thresholds of blood glucose  $\leq$ 70 mg/dL, the following subgroups will be analyzed using data collected from all randomized patients prior to discontinuation of IP through Week 26:

- age (<40,  $\geq40$  years)
- hemoglobin A1c stratum (≤8.5% vs. >8.5%)
- region
- type of basal insulin during the lead-in period (glargine U-100 vs. degludec U-100)
- prandial insulin dosing plan (carbohydrate counting or pattern adjustment)

The event rate and incidence will be analyzed using the same model specified in Table 6.5 with the addition of factors for subgroup, and 2-way interaction of subgroup and treatment. The 2-way interaction will be used to evaluate treatment by subgroup interaction.

#### 6.14. Interim Analyses and Data Monitoring

No interim analyses are planned for this study. If an unplanned interim analysis is deemed necessary, the appropriate Lilly medical director, or designee, will be consulted to determine whether it is necessary to amend the protocol.

#### 6.15. Clinical Trial Registry Analyses

Additional analyses will be performed for the purpose of fulfilling the Clinical Trial Registry (CTR) requirements.

Analyses provided for the CTR requirements include the following:

- Summary of AEs, provided as a dataset which will be converted to an XML file. Both Serious Adverse Events and 'Other' Non-Serious Adverse Events are summarized by treatment group and MedDRA PT.
- An AE is considered 'Serious' whether or not it is a TEAE.
- An AE is considered in the 'Other' category if it is both a TEAE and is not serious. For each Serious AE and 'Other' AE, for each term and treatment group, the following are provided:
  - the number of participants at risk of an event
  - the number of participants who experienced each event term
  - the number of events experienced.
- Consistent with www.ClinicalTrials.gov requirements, 'Other' AEs that occur in fewer than 5% of patients/subjects in every treatment group may be excluded if a 5% threshold is chosen. Allowable thresholds include 0% (all events), 1%, 2%, 3%, 4%, and 5%.
- Adverse event reporting is consistent with other document disclosures for example, the CSR, manuscripts, and so forth.

# 7. Novel Coronavirus (COVID-19) Impact

This section lists some of the potential statistical analyses may be performed at the final database lock due to the impact of COVID-19 pandemic, if data guarantee.

#### 7.1 Patients' Study Visits Impacted by COVID-19

Percentage and count of randomized participants with study visits impacted by COVID-19 will be compared by treatment groups. These participants includes, but not limited to six kinds, patients with any visit not performed, patients with any on-site visit changed to remote, patients with HbA1C missing, patients with 1,5 AG result missing, patients with MMTT result missing and patients with direct to patient drug supply. Listing of patients with study visits impacted by COVID-19 will also be provided.

For each of the six situations, a separate summary table and listing will be provided.

# 7.2 Protocol Deviation

Percentage and count of randomized participants having protocol deviation related to COVID-19 pandemic will be summarized by treatment. No statistical comparison between treatment groups will be conducted.

A listing of all randomized participants having protocol deviation due to COVID-19 pandemic will be provided.

A summary table and listing of all randomized participants having significant protocol deviation due to COVID-19 pandemic will also be provided.

# 7.3 Patient Disposition

A summary table for dispositon reasons of all enrolled participants who discontinue study during the lead-in period due to COVID-19 may be provided. For the treatment period, a summary table for dispositon reasons of all randomized participants who discontinue study or study treatment due to COVID-19 may be provided. For the safety follow-up period, a summary table for dispositon reasons of all randomized participants in the safety follow-up period who discontinue study due to COVID-19 may be provided.

# 7.4 COVID-19 Infection

Percentage and count of randomized participants having COVID-19 infection, including death due to COVID-19 pandemic from lead-in period to safety follow-up period will be summarized by treatment.

A listing of randomized participants who had COVID-19 infection, including death due to COVID-19 infection, from lead-in period to safety follow-up period will be provided.

# 7.5 Some Mitigation Procedures

Some mitigation procedures are conducted to reduce the impact of COVID-19 during the study, which include direct to patient drug supply, IP (bolus insulin) local purchase and Visit 7 and Visit 8 combined.

Summary and listing of IP local purchase due to the COVID-19 pandemic will be provided. Randomized participants with Visit 7 and Visit 8 combined due to the COVID-19 pandemic will be summarized by treatment.

#### 7.6 Sensitivity Analysis for Efficacy

The impact of COVID-19 on the efficacy of IP on the patients may come from different aspects such as prolonged treatment interruptions due to COVID-19 illness or control measures, study or treatment discontinuations due to COVID-19 illness or control measures, death due to COVID-19 and the usage of protocol prohibited medications to treat COVID-19.

A sensentivity analysis will be conducted on the randomized patients without essential impact of COVID-19, i.e., the randomized patients who can't be classified into the above two groups. The MMRM and ANCOVA models as described in Section 6.11.1 and Section 6.11.3 respectively will be repeated as the models for the sensitivity analysis. If the conclusion differs from that of all randomized patients, the data and analysis will be further investigated.

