#### 5.2. Determination of Sample Size

Patients will be randomized in a 1:1 ratio to double-blind LY900014 dosed 0 to 2 minutes before meals, or double-blind insulin lispro dosed 0 to 2 minutes before meals. Assuming a noninferiority margin (NIM) of 0.4%, no true difference between treatment arms, and a standard deviation (SD) of 1.1%, approximately 298 completers (149 in each treatment group) will provide 87% power to show noninferiority between LY900014 and insulin lispro in change from baseline to 26 weeks in hemoglobin A1c (HbA1c) using the upper limit of a 2-sided 95% confidence interval (CI; LY900014 – insulin lispro). Assuming a 15% dropout rate for 26 weeks, approximately 350 patients will need to be randomized.

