## 6. A Priori Statistical Methods

#### 6.1. General Considerations

Statistical analysis of this study will be the responsibility of Eli Lilly and Company (hereafter Lilly). Any change to the data analysis methods described in the protocol will require an amendment ONLY if it changes a principal feature of the protocol. Any other change to the data analysis methods described in the protocol, and the justification for making the change, will be described in this SAP and/or in the clinical study report (CSR). Additional exploratory analyses will be conducted, as deemed appropriate.

For purposes of analysis, the following populations are defined in Table 6.1.

Population	Description		
Entered	All patients who give informed consent.		
Enrolled	All patients who receive at least 1 dose of open-label insulin lispro in the 8-week lead- in period.		
Randomized	All patients who are randomly assigned to study treatment at Visit 8. Treatment group will be defined on the basis of the treatment the patients are assigned.		
Safety	All randomized patients who receive at least 1 dose of the randomly assigned investigational product (IP). Treatment group will be defined on the basis of the treatment the patients are assigned.		
Completer	Patients included in the randomized population who have completed Week 26 of study treatment without permanent discontinuation of IP. Treatment group will be defined on the basis of the treatment the patients are assigned.		
Per Protocol	Patients included in the randomized population who have completed Week 26 of study treatment without permanent discontinuation of IP and without significant protocol deviations through Week 26 that would significantly impact the primary objective. Treatment group will be defined on the basis of the treatment the patients actually receive.		

Table 6.1.Patient Populations

Unless otherwise stated, the efficacy analyses will be conducted on the Randomized Population, and the safety analyses will be conducted on the Safety Population.

The primary analysis is for the treatment period through Week 26.

Unless otherwise noted, all tests of treatment effects will be conducted at a 2-sided alpha level of 0.05, and CIs will be calculated at 95%, 2-sided. All tests of interactions between treatment groups and other factors will be conducted at a 2-sided alpha level of 0.10.

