#### 6.11. Efficacy Analyses

#### 6.11.1. Primary Outcome and Methodology

The primary objective of this study (H1) is to test the hypothesis that LY900014 is noninferior to insulin lispro on glycemic control (NIM=0.4% for HbA1c) in patients with T1D, when administered as prandial insulin (0-2 minutes prior to the meal), in combination with basal insulin for 26 weeks.

The primary efficacy comparison will be based on the contrast between LY900014 and insulin lispro at Week 26 (Visit 18) from the MMRM analysis of change from baseline in HbA1c including data collected from all randomized patients prior to discontinuation of IP through Week 26. The model for the analysis of the primary efficacy endpoint of change from baseline in HbA1c will include the fixed class effects of treatment, strata (country, type of basal insulin, use of metformin at study entry), visit, and treatment-by-visit interaction, as well as the continuous, fixed covariates of baseline value. An unstructured covariance structure will be used to model the within-patient errors. Significance tests will be based on LS means and Type III tests. If this analysis fails to converge, the following covariance structures will be tested in order:

- Toeplitz with heterogeneity
- autoregressive with heterogeneity
- compound symmetry with heterogeneous variances
- Toeplitz
- autoregressive
- compound symmetry without heterogeneous variances

The first covariance structure that converges will be used. The Kenward-Roger approximation will be used to estimate denominator degrees of freedom.

LY900014 will be declared noninferior to insulin lispro if the upper limit of the 2-sided 95% CI for the LS mean difference in the change from baseline in HbA1c for LY900014 minus insulin lispro is below +0.4%.

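### The COVID-19 sensitivity analysis drops whole patients for post-randomization events under an undefined rule, so a differing result would not isolate the effect of COVID-19

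*SAP*

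**What the plan says.** SAP 7.6 names four ways in which COVID-19 may affect efficacy: prolonged treatment interruption, "study or treatment discontinuations due to COVID-19 illness or control measures, death due to COVID-19", and use of protocol-prohibited medication to treat the infection. It then sets the analysis population: "A sensentivity analysis will be conducted on the randomized patients without essential impact of COVID-19". Membership is explained as not falling into two groups said to be described above, but no two groups are described. The terms for an essential impact and a prolonged interruption are not defined either.

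The MMRM of SAP 6.11.1 and the LOCF ANCOVA of 6.11.3 are refitted on that subset. A differing conclusion prompts further investigation. No rule keeps an excluded patient's HbA1c from before the event.

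The primary MMRM is defined as "including data collected from all randomized patients prior to discontinuation of IP through Week 26". SAP 6.1 counts laboratory values as on IP up to 14 days after the last dose. Protocol 8.1.1 lists, among the grounds for permanent discontinuation of IP, use of prohibited concomitant medication and more than 14 consecutive days without IP.

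**The concern.** The analysis should show whether COVID-19 altered the noninferiority conclusion. For randomized patients the listed impacts arise essentially after randomization, and some of them (interruption, discontinuation) can depend on treatment and on glycaemic control. Removing patients on that basis gives up the protection that randomization provides for this analysis. It also removes Week 4, 8 and 12 HbA1c values that the MMRM could use.

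If the result then differs from the primary one, three explanations are mixed: an effect of COVID-19 on the measurements, selection of patients, and a smaller sample. No other planned analysis separates them. The Per Protocol and Completer analyses also select on what happened after randomization, and SAP 6.11.4 plans no sensitivity analysis for missing data.

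**Working it through.** **1. Reproduce the design figures (SAP 5.2, 6.1).** Inputs: "Assuming a noninferiority margin (NIM) of 0.4%, no true difference between treatment arms, and a standard deviation (SD) of 1.1" (HbA1c, in %); "Patients will be randomized in a 1:1 ratio"; "all tests of treatment effects will be conducted at a 2-sided alpha level of 0.05".

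- SE = 1.1 × √(2/149) = 0.1274.
- Power = Φ(0.4/0.1274 − 1.96) = 88.1% (87.9% with the noncentral t, 296 df). The SAP says "approximately 298 completers (149 in each treatment group) will provide 87% power", so this agrees closely.
- N = 298/0.85 = 350.6, that is 351. The SAP says "Assuming a 15% dropout rate for 26 weeks, approximately 350 patients will need to be randomized", which agrees.

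**2. What the exclusion removes beyond the primary analysis.**

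| Impact in SAP 7.6 | Later HbA1c in the primary MMRM? |
|---|---|
| Study or treatment discontinuation, death | Already out, apart from the 14-day laboratory window |
| Prohibited medication | Already out if Protocol 8.1.1 is followed, apart from the same window |
| Interruption of more than 14 consecutive days | Already out if Protocol 8.1.1 is followed, apart from the same window |
| Interruption of 14 days or less (if it counts as prolonged) | Still in, since Protocol 8.1.2 allows IP to resume |

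In the first three rows, deleting the patient mainly removes values from before the event.

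**3. How many earlier values.** HbA1c visits are at Weeks 4, 8, 12 and 26. Assume event times uniform over 26 weeks. The mean number of values before the event is (22 + 18 + 14 + 0)/26 = 2.08 of 4, and 22/26 = 85% of affected patients have at least one. The affected share is not stated. At 10% of 350 (35 patients) about 35 × 54/26 = 73 values are lost; at 20%, about 145. These counts ignore other missing data.

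**4. Possible shift from selection.** Let f1 and f0 be the excluded shares on LY900014 and lispro, and d the amount by which excluded patients' HbA1c change is worse than that of retained patients (same d in both arms). Each retained mean lies f × d below the full-arm mean, so the difference shifts by −(f1 − f0) × d.

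- Balanced exclusion: 0.
- f1 − f0 = 0.10, d = 0.3: −0.03. With d = 1.0: −0.10. The direction favours LY900014; it reverses if more lispro patients are excluded.

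**5. Precision: deletion against censoring.** Generalized least squares information at Week 26, 175 per arm, SD 1.1, 15% other dropout, uniform event times, known covariance with correlation ρ between adjacent visits decaying by visit order, averaged over 200 simulated patterns. At ρ = 0.7:

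| Affected | SE, whole patient deleted | SE, later values censored | Ratio | Power, deleted vs censored |
|---|---|---|---|---|
| 10% | 0.1309 | 0.1289 | 1.016 | 86.3% vs 87.4% |
| 20% | 0.1390 | 0.1345 | 1.033 | 82.0% vs 84.5% |
| 30% | 0.1492 | 0.1415 | 1.054 | 76.5% vs 80.7% |

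At 20% affected the ratio is 0.1411/0.1390 = 1.015 for ρ = 0.5 and 0.1366/0.1291 = 1.058 for ρ = 0.85.

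**The case against.** The strongest objection is that the remedy nearly reproduces the primary analysis. If Protocol 8.1.1 is followed, most post-impact values are already out, so censoring them again changes little and tests little. This stands as a limit on what the censored analysis can show. It does not support the planned version: where few on-IP values follow the impact, the planned analysis differs from the primary mostly through selection and lost data.

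Second, Section 7 presents its analyses as potential, no claim depends on 7.6, and the trial is double-blind. SAP 7.1 compares impacted visits by treatment group, and 7.2 and 7.4 summarize deviations and infections by treatment, so much of any imbalance would be visible. All of this stands and keeps the point minor.

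Third, restriction to an unaffected subset resembles the Per Protocol and Completer analyses. It does, but those share the same weakness and so cannot supply what is missing.

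Fourth, values from before a recorded impact date need not be clean, because control measures may have started earlier. This is fair, and it is a reason to define the start date carefully.

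Two stronger readings are tempting. A reader might infer that the trial's randomized comparison is broken. The documents do not support that, because the confirmatory analysis in 6.11.1 uses all randomized patients. A reader might also take 1/√(1 − x), that is 2.6%, 5.4% and 11.8% at x = 5%, 10% and 20%, as precision that the remedy recovers. That formula compares deletion with complete data on the affected patients, whereas under censoring they also lack Week 26 values.

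**Conclusion.** The point holds as a minor defect in a supportive analysis. SAP 7.6 selects patients on post-randomization events through a rule that cannot be reproduced from the text, and a result that differs from the primary one could not be attributed to COVID-19.

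Bias is possible, not established. It needs exclusion related to both arm and outcome, and the documents give no sign of that. Under the assumed 10-point imbalance the shift is a small to moderate part of the 0.4 margin (0.03/0.4 = 7.5% to 0.10/0.4 = 25%). The precision at stake is small. The main gain from changing the analysis is that all randomized patients stay in the comparison.

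The affected share, event timing, within-patient correlation, imbalance and d are assumptions. The overlap with the primary analysis rests on Protocol 8.1.1 being followed.

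**What to change.** Amend SAP 7.6 before unblinding:

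1. Replace the reference to two groups with explicit COVID-19 impact categories, including what counts as prolonged and as essential.
2. Define an impact start date for each affected patient, tied to when the impact began and not to when it was recorded.
3. Keep all randomized patients, set to missing only HbA1c values after that date that still count as on IP, and refit the 6.11.1 MMRM.
4. Retain the patient-exclusion MMRM and ANCOVA as descriptive only, and report exclusions by arm and category beside them.

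The cost is SAP wording and one derived date per affected patient. SAP 7.1 to 7.5 plan summaries and listings but do not promise such a date, and none is specific to interruptions or prohibited medication, so availability must be checked. The result may lie close to the primary analysis when few on-IP values follow the impact. The report should give the number of values set to missing so that such closeness is not over-read as evidence of robustness.

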8.1.1. Permanent Discontinuation from Study Treatment

Patients will be discontinued from the IP in the following circumstances:

- The investigator may decide that the patient should stop IP. If this decision is made because of an AE, SAE, or a clinically significant laboratory value, the study drug is discontinued for that patient and appropriate measures are to be taken. Lilly or its designee is to be alerted.
- The patient requests to discontinue IP.
- If the patient becomes pregnant.
- If an investigator, study site personnel performing assessments, or patient is unblinded, the patient must discontinue IP.
- If the patient, for any reason, requires treatment with another therapeutic regimen or therapeutic agent that has been demonstrated to be effective for treatment of the study indication. Discontinuation from IP should occur prior to introduction of the new agent.
- Use of prohibited concomitant medication (see Table ITSD.8).
- If the patient has not taken IP for more than 14 consecutive days.
- **Discontinuation due to a hepatic event or liver test abnormality.** Patients who are discontinued from investigational product due to a hepatic event or liver test abnormality should have additional hepatic safety data collected via CRF.

Discontinuation of the investigational product for abnormal liver tests **should be** considered by the investigator when a patient meets one of the following conditions after consultation with the Lilly designated medical monitor:

- alanine aminotransferase (ALT) or aspartate aminotransferase (AST) >8X upper limit of normal (ULN)
- ALT or AST >5X ULN for more than 2 weeks
- ALT or AST >3X ULN and total bilirubin level (TBL) >2X ULN or international normalized ratio (INR) >1.5
- ALT or AST >3X ULN with the appearance of fatigue, nausea, vomiting, right upper-quadrant pain or tenderness, fever, rash, and/or eosinophilia (>5%)
- alkaline phosphatase (ALP) >3X ULN
- ALP >2.5X ULN and TBL >2X ULN
- ALP >2.5X ULN with the appearance of fatigue, nausea, vomiting, right quadrant pain or tenderness, fever, rash, and/or eosinophilia (>5%)

Patients discontinuing from the investigational product prematurely for any reason should complete adverse event and other follow-up procedures per Section 2 (Schedule of Activities), Section 9.2 (Adverse Events), and Section 9.4 (Safety) of this protocol.

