8.1.2. Temporary Discontinuation from Study Treatment

During the study, patients who temporarily discontinue the IP may be able to resume IP based on the following scenario:

Patient has not taken IP for 14 consecutive days or less:

• If the treatment regimen restarts within 14 days of when the patient initially stopped taking IP, patient may continue in the study and begin treatment again with IP. During this time, nonstudy insulins may have been used. If the patient decides to continue in the study, no early termination procedures will be completed. Patients will continue study visits through the safety follow-up.

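### Does the undefined pair of groups in the SAP's COVID-19 sensitivity analysis leave the analysis set open enough to need a change?

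*SAP*

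**What the plan says.** SAP 7.6 (Sensitivity Analysis for Efficacy) first describes how COVID-19 might affect efficacy. It gives four examples:

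- "prolonged treatment interruptions due to COVID-19 illness or control measures"
- study or treatment discontinuation for the same reasons
- death due to COVID-19
- "the usage of protocol prohibited medications to treat COVID-19"

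The next paragraph restricts the analysis to randomized patients without essential COVID-19 impact and explains this as those who cannot "be classified into the above two groups". The MMRM of SAP 6.11.1 and the ANCOVA of SAP 6.11.3 are then repeated in that set. The consequence is: "If the conclusion differs from that of all randomized patients, the data and analysis will be further investigated".

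The introduction to SAP Section 7 says that it lists "some of the potential statistical analyses may be performed at the final database lock", although 7.6 itself states this analysis as one that will be done.

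Two protocol sections bear on the categories. Section 8.1.1 lists among the grounds for permanently stopping investigational product (IP) the use of a prohibited concomitant medication, and "If the patient has not taken IP for more than 14 consecutive days". Section 8.1.2 covers shorter gaps: "If the treatment regimen restarts within 14 days of when the patient initially stopped taking IP, patient may continue in the study".

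**The concern.** The rule that decides who is in the analysis points to something that does not exist: four kinds of impact are named, two groups are referred to, and none is defined. Because the second phrase is offered as the explanation of the first, it reads as the operative definition, and taken literally it cannot be programmed.

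The word prolonged adds a second gap. If it means more than 14 days, protocol 8.1.1 already turns the interruption into a discontinuation and the first example duplicates the second. If it means something shorter, no cut-off is given, and patients who resumed under 8.1.2 could be kept or dropped.

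Membership depends on events after randomization, so a set chosen with the treatment codes known could be steered. What would be at stake is the credibility of one robustness check on the noninferiority result.

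**Working it through.** **1. Is there a pair of groups that the text could mean?** The candidates in SAP Section 7 are:

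| Place | What is classified | Number |
|---|---|---|
| 7.1 | kinds of affected visit | 6 |
| 7.3 | study periods for disposition | 3 |
| 7.5 | mitigation procedures | 3 |
| 7.6 | examples of impact on efficacy | 4 |

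None is a pair. Illness versus control measures is a pair, but of causes, not of patients. The phrase is therefore a leftover or a miscount, and nothing in the section shows a redaction that would explain it.

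**2. How far do the plausible readings differ?** Set the four examples against protocol 8.1.1:

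- Discontinuation of study or treatment ends IP by definition.
- Death ends participation, so it is also a discontinuation due to COVID-19.
- Prohibited medication is a listed ground: "Use of prohibited concomitant medication (see Table ITSD.8". That table allows limited emergency use of some insulins and limited use of systemic glucocorticoids, so the overlap is large but not complete.
- An interruption longer than 14 consecutive days is a permanent discontinuation.

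Reading A excludes patients with any of the four. Reading B excludes only those with the first two, interruption or discontinuation. If sites follow 8.1.1, the deaths and nearly all the prohibited-medication cases fall under discontinuation, so A and B give almost the same set. Reading C, only the last two, would keep patients who stopped treatment because of COVID-19 in a set described as free of essential COVID-19 impact. That defeats the stated purpose.

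The main remainder is patients who resumed after a gap of 14 days or less.

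**3. Scale of the remainder (illustration).** Inputs from SAP 5.2: SD 1.1, 149 completers per arm, margin 0.4, true difference 0, two-sided 95% interval.

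The plan's own figure first. The standard error is 1.1 × √(2/149) = 0.1274. Power = Φ(0.4/0.1274 − 1.96) = Φ(1.18) = 0.881 (0.879 with the noncentral t). The stated 87% is reproduced to within about a point.

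The documents give no number of short gaps. Assume a fraction f in each arm, and a treatment difference in those patients 0.4 points away from the rest. Keeping rather than dropping them shifts the estimate by f × 0.4. Dropping them gives a half-width of 1.96 × 1.1 × √(2/(149(1 − f))).

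| f (assumed) | Patients per arm | Shift (points) | Half-width if dropped |
|---|---|---|---|
| 0 | 0 | 0 | 0.250 |
| 2% | about 3 | 0.008 | 0.252 |
| 5% | about 7 | 0.020 | 0.256 |
| 10% | about 15 | 0.040 | 0.263 |

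**4. Scale if more patients are excluded for any reason.** With the same inputs, excluding an assumed 5%, 10%, 20% or 30% of the 298 leaves about 283, 268, 238 or 209 patients. Power within the sensitivity set is then 0.86, 0.85, 0.80 or 0.75. The primary analysis keeps its own power throughout.

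These figures are for completers, whereas 7.6 runs on randomized patients. Patients who stopped IP also contribute their earlier HbA1c values, so the tables show an order of size and do not estimate the effect.

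**The case for a change.** The best case for a change is that two programmers could build different sets and both claim to follow the SAP. The four impacts are introduced as examples, so the list may not be closed. For instance, 7.6 does not say whether a patient whose HbA1c is missing because of COVID-19 (a category in SAP 7.1) counts as affected. Patients who stopped IP after at least one postbaseline HbA1c still enter the primary MMRM under Table 6.2, so removing or keeping them can move the estimate. SAP 6.11.4 plans no sensitivity analyses for missing data, which leaves few robustness checks. The fault could also be mended in a sentence.

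Much of this is accurate. The phrase is wrong, the list is open, and the length is missing. Three things limit the weight. First, the governing idea, patients without essential COVID-19 impact, is stated, and it leads an analyst to the any-of-these reading. Second, other checks cover related ground. SAP 6.11.3 repeats the MMRM in the Completer and Per Protocol populations, which already leave out permanent IP discontinuations whatever their cause, and it adds an LOCF ANCOVA. SAP 7.1 to 7.4 provide COVID-19 summaries and listings, some of them optional. Third, the obvious rewording is not neutral. Listing the four as the full definition would close a list that the SAP leaves open. Tying prolonged to the 14-day rule would make that category redundant with discontinuation.

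**Conclusion.** This is a drafting slip with a missing detail that analysts can fill sensibly, and it does not call for a change to the plan. The working definition is to exclude randomized patients with any of the named COVID-19 impacts. Fixing that definition while the codes are still blinded, including how resumed short gaps are handled, is ordinary dataset specification. SAP 6.1 already allows details of analysis method and their justification to be described in the clinical study report.

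The reach is one supportive HbA1c analysis. No alpha, sample size, population for the primary test or noninferiority decision depends on it, and a discrepant result leads only to further investigation. The documents give no counts, so the true effect cannot be stated. On the assumed 2% to 10% of short gaps it is at most 0.040 points on a 0.4 margin.

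The conclusion rests on sites applying protocol 8.1.1 as written, and on the set being settled before treatment codes are known. If the set were chosen after unblinding, the steering concern would have real force, but the wording in 7.6 does not itself imply that.
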